strategies. (8) Non-pharmacologic and non-opioid therapy is the preferred treatment option for chronic non-cancer pain. Opioids should only be used when the benefits for pain and function outweigh the risks. Providers should establish realistic treatment goals for pain and function and monitor for recovery; prescribe immediate release opioids instead of long acting opioids; prescribe the lowest effective dose; assess benefits and risk of doses >50 MED; and re-evaluate the benefits and harms of opioid therapy every 3 months or more frequently. Providers should also conduct periodic risk assessments and incorporate mitigation strategies into the management plan; review state prescription drug monitoring program data when available; perform urine drug testing at least annually; and avoid co-prescribing benzodiazepines. Finally, patients with opioid use disorder should be referred to evidence-based treatment programs (e.g. Suboxone therapy for addiction). Although the CDC and other guidelines provides recommendations on what to do for safe prescribing of opioids (7-10), they do not provide guidance on how to translate them into practice at the point of care.

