We will compare between study groups (EMR CDS guided care vs. EMR CDS+ stepped opioid CCM) the changes in the outcome measures listed in Table 1. The *main study outcomes* are changes in the average daily opioid dose (morphine equivalent dose, MED) and percentage of patients with average daily opioid dose

>90 MED. *Secondary outcomes* include changes in annual rates of service utilization; process of care measures; patient reported outcomes; and provider reported measures.

C.7.1 EMR and claims data variables: Table 1 describes the data sources and frequency of data collection for each study variable. Most data collected for this study will be derived from Epic electronic health records and claims data. Ochsner Enterprise Data Warehouse (EDW) is a relational database that captures and stores data from Epic and Ochsner’s claims data warehouse. A unique identification number is assigned to each patient and it links all data regardless of location within EDW. We have the ability to

TABLE 1	Outcome Measure	Data Source	Frequency
Main Study Outcomes			
Morphine equivalent daily dose (MEDD)	Average daily opioid dose	EMR & Claims	Quarterly
	% patients prescribed high dose (>90 MED)	EMR & Claims	Quarterly
	% patients prescribed high dose (>50 MED)	EMR & Claims	Quarterly
Secondary Outcomes			
Service utilization	Inpatient hospitalization rates	EMR & Claims	Annually
	Emergency department use rates	EMR & Claims	Annually
	Medical and pharmacy costs	EMR & Claims	Annually
Process of care	% Specialty referrals	EMR	Quarterly
	% Pain agreements documented	EMR	Quarterly
	% Urine drug screening documented	EMR	Quarterly
	% Naloxone documented	EMR	Quarterly
	% Non-opioid prescriptions written	EMR	Quarterly
Patient reported outcomes	PEG 3-Item Pain Score	EMR	Quarterly
	Patient Health Questionnaire, PHQ-4 Score	EMR	Quarterly
	PROMIS-10, COMM-9, PGIC	EMR	Quarterly
Physician reported measures	Provider Experience with Mental Health Care Management	Redcap survey	Annually

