#### **5. Statistical Analysis**

Outcomes data were observed and collected in two time periods, pre-index and post-index. For the behavioral health group, the index date was defined as the date of enrollment during the study recruitment period (April 2019 to December 2021). For EMR-CDS usual care group, the index date is the first date within the study enrollment period at which a patient had been prescribed opioid medications for 90 of the previous 120 days.

Potential participants in the control arm of the study were identified from the chronic opioid health maintenance registry within the electronic health record system and propensity score matched to patients enrolled in the behavioral health arm. Baseline variables in the propensity score model were age at index event date, sex, race/ethnicity, average MEDD, anxiety, depression, and Charlson comorbidity index score. Average MEDD was calculated from opioid medication orders in the 12-month pre-index period. MEDD is calculated by determining the total daily amount of a prescribed opioid, multiplying the dose of the opioid by a conversion factor to ascertain morphine milligram equivalents and then adding up the converted dosage. Anxiety, depression, and Charlson comorbidity scores were determined from pre-index encounter diagnoses, historical problem lists, and PHQ-9/GAD-7 scores  $>10$  documented within the electronic health record.

Study outcomes were observed and collected in two 12-month time periods defined relative to the index date, pre-index and post-index, resulting in a 2-dimensional vector of repeated measures for each outcome from each patient. All outcome models for repeated measures incorporate a random effect with unstructured covariance matrix to model within-patient variability. It was assumed that patients remained in the health system from their first observed encounter through the end of the study period. A difference-in-difference approach was utilized in which outcomes were assessed as the change in group differences from pre- to post-

index. The model included fixed effects for study group, time (pre-index, post-index), and the group-by-time interaction.

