Repeat measured outcomes include average MEDD,  $\text{MEDD} \geq 50$ ,  $\text{MEDD} \geq 90$ , and service utilization (inpatient/emergency department). These repeated outcomes are evaluated using the generalized linear mixed model approach described above with fixed effects as defined for the model. MEDD categorial outcomes are evaluated via mixed effects logistic regression models with estimates of odds ratios and difference-in-difference ratios (ratio of odds ratios). Mixed effects negative binomial regression models are used for assessing group differences in service utilization with rate ratios and difference-in-difference ratios (ratio of rate ratios).

Outcomes defined by first-time documentation of guideline concordant care for opioid risk mitigation are also evaluated using logistic regression. These outcomes are not repeated measures as they are only assessed post-index among patients with no pre-index documentation. Thus, time effects and random patient effects are omitted from the generalized linear model when evaluating new occurrences of guideline concordant care for opioid risk mitigation. The resulting logistic regression models include a single fixed effect for study group and no random effects.

Analyses were carried out using SAS version 9.4 for Windows, group comparisons are evaluated at significance level 0.05, and all estimates are presented with 95% confidence intervals.

**Ochsner Clinic Foundation  
Institutional Review Board**  
[name]  
[contact] | [[contact]](mailto:[contact])  

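### First-time guideline-care outcomes are compared in subsets where the propensity match no longer assures balance; for urine screening, patients re-tested as the guideline recommends are also left out

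*SAP*

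**What the plan says.** SAP 1.4.1 lists five secondary comparisons that count only first-time documentation after the index date: pain agreement, urine drug screening, naloxone order, referral to a specialist outside mental and behavioral health, and anti-depression medication. SAP section 5 explains that "they are only assessed post-index among patients with no pre-index documentation", and continues: "The resulting logistic regression models include a single fixed effect for study group and no random effects".

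The same section describes how the groups were formed. Registry patients were "propensity score matched to patients enrolled in the behavioral health arm". The score is specified in one sentence: "Baseline variables in the propensity score model were age at index event date, sex, race/ethnicity, average MEDD, anxiety, depression, and Charlson comorbidity index score". No matching ratio is given. No re-matching, weighting or balance check is planned within the restricted sets. The repeated outcomes (dose and service use) are handled differently, with terms for group, period and their interaction over two 12-month windows.

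Protocol A.3 reports that the guideline asks providers to "perform urine drug testing at least annually". Protocol Table 1 lists the process measure as the percentage with "Urine drug screening documented", collected quarterly, and mentions no first-time restriction.

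**The concern.** The match is the only stated control of confounding for these outcomes. It works on the full matched sample. Each guideline-care outcome then selects its own subset on a variable that was not matched, so one member of a matched set can leave while the other stays. A group-only model cannot repair any imbalance that results. These outcomes also lose the protection of the difference-in-difference model, which absorbs baseline group differences for the repeated outcomes.

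Urine screening raises a separate question of what is measured. A patient screened in the year before index and again in the year after has received the care that the guideline describes, but does not count at all.

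Receipt of risk-mitigation care is part of SAP Hypothesis 1, so these odds ratios support a stated claim of the trial.

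**Working it through.** **The plan's own figure.** The SAP's only sample size is for the primary outcome (20% vs 10%, odds ratio 2.25, 80% power). The log-odds-ratio formula with pooled proportion 0.15 and two-sided alpha 0.05 (the SAP does not state sidedness) gives (1.960 + 0.842)² / [0.15 × 0.85 × 0.25 × (ln 2.25)²] = 374.4, close to the stated 372. The design effect is 1 + (11 − 1) × 0.03 = 1.30. Then 372 × 1.30 = 483.6, rounded up to 490 = 35 × 14, or 245 per group. Attrition gives 245 / 0.85 = 288.2, so 289 per group and 578 in total. The figures reproduce, but no figure is given for the guideline-care outcomes.

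**Assumptions.** The share with earlier documentation is not in the documents; I take 30% to 70%. I also assume 1:1 matching and 245 pairs.

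**What the restriction leaves.** Patients kept per arm = 245 × (1 − f). Intact pairs, if documentation is independent within pairs, = 245 × (1 − f)². Power is for 30% vs 40%, two-sided 0.05.

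| f in both arms | Kept per arm | Intact pairs | Power |
|---|---|---|---|
| 0 | 245 | 245 | 0.64 |
| 30% | 172 | 120 | 0.49 |
| 50% | 122 | 61 | 0.37 |
| 70% | 74 | 22 | 0.24 |

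With positive correlation within pairs, more pairs survive, up to the number kept per arm. The power column treats patients as independent, although the 245 already contains the 1.30 inflation, so it is optimistic.

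**Whether balance can fail.** Take a risk factor present in 50% of both arms, post-index documentation of 20% without it and 60% with it, and no treatment effect. In the full sample both arms have 0.5 × 0.2 + 0.5 × 0.6 = 0.40, so the odds ratio is 1.00. Now exclude patients with earlier documentation, at the shares shown (without / with the risk factor).

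| Usual care | Collaborative care | Post-index rate, usual vs collaborative | Odds ratio |
|---|---|---|---|
| 20% / 40% | 20% / 40% | 0.371 vs 0.371 | 1.00 |
| 20% / 40% | 30% / 70% | 0.371 vs 0.320 | 0.80 |
| 20% / 40% | 40% / 80% | 0.371 vs 0.300 | 0.73 |
| 10% / 30% | 40% / 90% | 0.375 vs 0.257 | 0.58 |

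Second row in full. Usual care keeps 0.5 × 0.8 = 0.40 and 0.5 × 0.6 = 0.30, so the rate is (0.40 × 0.2 + 0.30 × 0.6) / 0.70 = 0.371. Collaborative care keeps 0.35 and 0.15, so the rate is (0.35 × 0.2 + 0.15 × 0.6) / 0.50 = 0.320. The odds ratio is (0.320 / 0.680) / (0.371 / 0.629) = 0.80. Swapping the arms inverts these ratios, so the direction is not fixed.

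**Urine screening.** Let q be the share screened before index, r the share of those re-screened, and s = 30% the share of the others newly screened. The share of post-index screened patients who are not counted is qr / [qr + (1 − q)s]. For q = 30%, r = 50% this is 0.15 / 0.36 = 42%. For q = 70%, r = 90% it is 0.63 / 0.72 = 88%. All three inputs are assumptions.

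**The case against.** The restriction uses a pre-index characteristic, so it defines a baseline subgroup and is not selection on something that treatment caused. It also holds fixed a plausible predictor of later documentation that the match left open. The first row of the second table shows no bias when the pattern is shared. This stands, and it limits the claim to what could happen.

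A reader might infer four stronger points that the documents do not support.

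- **That the odds ratios are confounded.** Bias needs earlier documentation to relate to risk differently by arm. No rates by arm are given, and the three patterns above are invented. The loss of patients and power shows reduced precision, not bias.
- **That the different index dates make earlier documentation likely to differ by time under decision support.** Decision support went live system-wide in October 2017 (Protocol C.1), and the earliest enrolment is April 2019. Every 12-month pre-index window therefore starts in April 2018 or later, wholly under decision support in both arms. Unequal exposure arises only if earlier documentation means any earlier time, which the SAP does not settle.
- **That Table 1 defines the outcome as a percentage of all patients.** It states no denominator. It only lacks a first-time restriction.
- **That all five outcomes should be redefined.** Annual repetition is documented for urine testing only. The SAP chose first-time documentation deliberately, and that suits a standing item such as a pain agreement. Extending the all-patient analysis to the others is a preference.

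**Conclusion.** The concern holds in limited form. The restriction and the group-only model are explicit, and the match contains none of the five items, so balance is not assured in the subsets and no step restores or checks it. Whether the odds ratios are biased is unknown. In the illustration they range from no shift to 0.58–0.80 with no true effect, depending wholly on assumed patterns.

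For urine screening the conflict is firmer, because the definition drops patients who were re-tested as the guideline recommends. How many depends on rates that the documents do not give (42–88% of those screened post-index under the assumptions above).

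All five are secondary outcomes, and the primary dose analysis is not restricted in this way.

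**What to change.** **(a) Urine drug screening.** Make the main analysis one in all matched patients. Either use the SAP's own group-by-time model over the two 12-month windows, or model post-index screening (yes/no) adjusted for pre-index screening and the seven propensity variables. Name one of these in advance. Keep new screening only as a supporting analysis.

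**(b) The other four outcomes.** Keep the first-time definition, but adjust for the seven propensity variables. Where events are few, enter the propensity score as a single term or weight within the subset. Report the number excluded and the covariate balance by arm for each outcome, and state whether earlier documentation means the 12-month window or any earlier time.

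**Cost.** SAP wording and a few more model terms; the covariates are already collected. The downside is sparse data. With 70% excluded, a 30% event rate gives about 2 × 73.5 × 0.30 = 44 events. Group plus seven covariates is at least eight terms, so about 44 / 8 = 5.5 events per term, which is why the single-term option is needed. Adjustment addresses imbalance on the seven variables only, not on factors outside them.

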C.3.2 Opioid Management and Mental/Behavioral Health Integration in Primary Care. Reducing practice variation in opioid management among primary care providers is a major priority. Strategies that work in the emergency department may or may not be as effective in primary care settings where providers have continuous relationships with their patients. Our team examined opioid prescription patterns in 36 primary care clinics and confirmed the urgency for integrating structured opioid management strategies in primary care. We conducted a prep-to-research query of prescriptions written within a 120-day period for long-acting opioids or 90-day supplies of short-acting opioids. We identified 2759 patients (1% of the 250,000 primary care patients served) who met our definition of chronic opioid therapy. Approximately 71% of these patients have chronic non-cancer pain, 62% have active diagnoses of depression/anxiety disorders, 56% have Medicare coverage, and 37% are age 65 years and older. We further observed that 6 clinics (located in 5 different geographic regions) each have more than 100 patients receiving chronic opioid therapy in contrast to all other sites.

[name] has extensive experience with *implementing structured opioid management* in primary care.(17, 24-30) His body of work includes developing tools to assess patient opioid misuse (Current Opioid Misuse Measure)(30), determine level of risk for substance abuse (Screener and Opioid Assessment for Pain Patients)(29), and adherence to terms of opioid agreements (Opioid Compliance Checklist). (26, 27) His research demonstrates that the combined use of risk assessments, compliance monitoring, specialty support with cognitive behavioral counseling improves patient outcomes.(24) Despite proven effectiveness of this approach to care, physician confidence or comfort with prescribing opioids remains a challenge necessitating ongoing collaborative care for pain management.

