### 1.4 Secondary

#### 1.4.1 Comparison of study groups

- Rate Ratio for average MEDD in post-index versus pre-index periods
- Inpatient hospital admission per 1000 patients
- Emergency Department visits per 1000 patients
- Odds Ratio for new post-index documented pain agreement
- Odds Ratio for new post-index documented urine drug screening
- Odds Ratio for new post-index documented naloxone prescription order
- Odds Ratio for new post-index documented referral to non-mental/non-behavioral health specialist
- Odds Ratio for new post-index documented anti-depression medications

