#### **4. Anticipated Effect Size, Power and Sample Size**

In the investigators' prior study on the clinical effectiveness of electronic medical record clinical decision support (EMR-CDS usual care) for opioid prescribing, approximately 20% of patients on chronic opioid therapy had an average daily opioid dose  $\geq 50$  MEDD. Using equal baseline response rate (RR) for the usual care and behavioral health collaborative care groups, a total sample size of 372 patients are required to detect an odds ratio of 2.25, corresponding to a 50% decrease in the collaborative care group (RR=10% vs 20% in usual care), with 80% power. The total sample size averaged 11 patients in each study group within each of 35 clinics. In accordance with the cluster randomized design, the variance inflation factor  $1 + (m - 1)\rho$  was incorporated, where  $m$  is the average cluster size ( $m=11$ ) and  $\rho$  is the intra-cluster correlation coefficient ( $\rho \leq 0.03$ ). Applying this inflation factor and rounding up to allow for equal group sizes across clusters resulted in a total sample size of 490 patients - 245 per group. Accounting for a potential 15% attrition rate, 578 total patients - 289 per group - were needed to attain the target sample size required to detect a 50% decrease in proportion of patients with average daily opioid dose  $\geq 50$  MEDD in the collaborative care group compared to the usual care group.

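### The SAP's first-documentation logistic models allow for no clustering, so their 5% level depends on a clinic mix that the plan does not secure

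*SAP*

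**What the plan says.** SAP 1.4.1 lists five comparisons of newly documented care after the index date: pain agreement, urine drug screen, naloxone, referral to a specialist outside mental and behavioral health, and anti-depression medication. One reads "Odds Ratio for new post-index documented naloxone prescription order". SAP section 5 explains that such outcomes are not repeated measures because "they are only assessed post-index among patients with no pre-index documentation". It therefore drops time and patient effects and concludes: "The resulting logistic regression models include a single fixed effect for study group and no random effects". Tests are at 0.05 with 95% confidence intervals, and no robust or clustered variance appears.

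Elsewhere the plan recognises clustering. SAP section 3 names region as the randomised cluster. SAP section 4 says "In accordance with the cluster randomized design, the variance inflation factor" was applied, over 35 clinics, with an average cluster size of 11 and a correlation of at most 0.03. Protocol C.8.1 says that its models will allow for design effects. Both of those passages concern opioid dose.

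On where patients come from:
- Protocol C.4.2 houses the service in five clinics but lets every clinic in a region refer.
- Protocol C.4.3 shows the referral prompt only to physicians who opt in.
- SAP section 5 says that controls were "identified from the chronic opioid health maintenance registry within the electronic health record system" and matched on patient characteristics: "Baseline variables in the propensity score model were age at index event date, sex, race/ethnicity, average MEDD, anxiety, depression, and Charlson comorbidity index score". Neither clinic nor region is among them.

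**The concern.** The reason given for dropping effects is that the data are not repeated. That disposes of the time and patient terms. It does not deal with patients who share a clinic, and clinic habits in ordering screens or naloxone are a plausible source of correlation in these outcomes.

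In the pre/post models, a clinic difference that is constant over time cancels in the contrast. The first-documentation models have no pre-index value, so such a difference goes straight into the group comparison whenever the two arms are spread differently over clinics. The plain standard error ignores this.

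At stake are the level and coverage of the tests that carry the risk-mitigation part of Hypothesis 1 in SAP section 2. That hypothesis gives urine screens, naloxone, functional assessments and specialty care as examples. It does not name pain agreements. That the anti-depression medication outcome falls under the same model is inferred from its parallel wording in 1.4.1.

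**Working it through.** **The plan's own chain.** With 20% versus 10%, odds ratio 2.25 and mean rate 0.15, the log-odds-ratio formula with null variance is N = 4(1.960 + 0.842)² / [0.15 × 0.85 × (ln 2.25)²] = 374.4, close to the stated 372. The inflation factor is 1 + (11 − 1) × 0.03 = 1.30, and 372 × 1.30 = 483.6. This becomes 490 = 7 × 2 × 35 after "rounding up to allow for equal group sizes across clusters". Per group, 245/0.85 = 288.2, rounded up to 289, so 578 in total. The sample size therefore assumes clinic correlation and an even spread of both arms over clinics.

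**Effect of ignoring clinic.** Let arm k have N_k patients, of whom n_kj are in clinic j, and let ρ be the within-clinic correlation. The ratio of true to plain variance is

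D = (1 − ρ) + ρ × S / (1/N₁ + 1/N₀), where S = Σ_j (n₁j/N₁ − n₀j/N₀)².

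The actual two-sided level of a nominal 5% test is 2[1 − Φ(1.96/√D)].

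**Inputs.** From the documents: 35 clinics, five hosts, ρ = 0.03 (SAP section 4), 245 per arm. Assumptions: 123 per arm if half the patients are excluded for pre-index documentation; 50% or 75% of enrollees from the host clinics; equal shares within hosts and within the other clinics. The host share of controls is 5/35 = 14.3% if spread evenly, or at least 500/2759 = 18.1% if the hosts are among the clinics of which Protocol C.3.2 says that they "each have more than 100 patients receiving chronic opioid therapy in contrast to all other sites" (likely, but not stated). A share of 35% is a further assumption.

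**One case in full (75% of enrollees, 14.3% of controls, 245 per arm).** Host clinics: 0.15 − 0.02857 = 0.12143 each. Other clinics: 0.25/30 − 0.02857 = −0.02024 each. S = 5 × 0.12143² + 30 × 0.02024² = 0.0860. With 1/(1/245 + 1/245) = 122.5, D = 0.97 + 0.03 × 0.0860 × 122.5 = 1.286. The level is 2[1 − Φ(1.728)] = 8.4%.

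| Host share, enrollees / controls | S | D (245) | Level, 245 per arm | Level, 123 per arm |
|---|---|---|---|---|
| even / even | 0 | 0.970 | 4.7% | 4.7% |
| 50% / 14.3% | 0.0298 | 1.079 | 5.9% | 5.3% |
| 50% / 18.1% | 0.0237 | 1.057 | 5.7% | 5.2% |
| 50% / 35% | 0.0053 | 0.989 | 4.9% | 4.8% |
| 75% / 14.3% | 0.0860 | 1.286 | 8.4% | 6.5% |
| 75% / 18.1% | 0.0755 | 1.247 | 7.9% | 6.3% |
| 75% / 35% | 0.0373 | 1.107 | 6.3% | 5.4% |

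At ρ = 0.01 the worst of these layouts has D = 0.99 + 0.01 × 0.0860 × 122.5 = 1.095, a level of 6.1%.

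**Simulation check.** Beta-binomial clinic rates were used, with an assumed 20% event rate, random allocation to clinics in the host layouts, no true effect and 20,000 to 40,000 replicates per scenario. At ρ = 0.03 and 245 per arm the plain test gave 4.5% to 4.8% when evenly mixed, 4.9% to 6.3% with 50% host enrolment and 6.6% to 8.7% with 75%. At 123 per arm the host layouts stayed between 4.9% and 6.7%. At ρ = 0.01 no layout exceeded about 6.3%.

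**Matched pairs.** Positive outcome correlation within pairs works the other way. With an assumed pair correlation of 0.04, the 50% to 75% layouts at ρ = 0.03 give 4.5% to 8.0% (245 per arm) and 4.8% to 5.8% (123). With 0.13 they give 3.8% to 6.2% and 3.7% to 5.0%. These runs keep every pair intact, so they overstate the offset where the pre-index exclusion breaks pairs.

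**The case against.** Much of the case against stands.

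- **Scope of the clustering statements.** A reader might infer that the protocol promised a clustering term for these models and that the SAP broke the promise. The documents do not support that. The inflation in SAP section 4 and the design-effects sentence in Protocol C.8.1 are both written for opioid dose. What remains is an inconsistency of approach: correlation is treated as real in one place and ignored in another.
- **The top of the range.** A reader might infer that these tests run at about 9%. That needs three quarters of enrollees from the hosts, few controls from them, no exclusion for pre-index documentation, the correlation at its stated ceiling and no pair correlation. Exclusions are to be expected, because the decision support had been live since October 2017 (Protocol C.4.1). Arms in separate clinics (D = 1.39, 9.6%) or all enrollees in the hosts with controls spread evenly (D = 1.60, 12.1%) would be worse, but the plan describes neither: every clinic in a region may refer.
- **Direction.** Even mixing makes the plain test slightly conservative, and matching may do so too.
- **Choice of variance.** Ranking one clustered estimator over another on assumed layouts is largely preference. A clustered variance also widens intervals without removing any imbalance in clinic mix. Clustering on clinic does not cover habits shared across a region, and the calculations above include no region-level variation.

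None of this supplies a reason for leaving clinic out of these models, or a feature of the plan that fixes the clinic mix.

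**Conclusion.** The omission is certain; its effect is not. The first-documentation models have no protection against clinic correlation, and the plan gives grounds for uneven mixing (five host clinics, physician opt-in, matching without clinic or region) without controlling it.

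At ρ = 0.03 and 245 per arm the level is about 4.7% when evenly mixed, about 5% to 6% with half the enrollees from host clinics, and about 7% to 9% with three quarters. The last case falls to about 6% to 7% at 123 per arm. At ρ = 0.01 every layout is at about 6.3% or less. These figures rest on assumed clinic shares and subset sizes, an assumed event rate in the simulations, and a correlation set for a different outcome. Pair correlation could cancel the inflation or reverse it.

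The exposure is limited to secondary outcomes. A reader might extend the point to the primary outcome, because the repeated-measures models also name only a patient effect. No inflation is claimed there, since time-constant clinic differences cancel in the pre/post contrast. Severity is minor to should-fix.

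**What to change.** In SAP section 5, keep the logistic model with study group, but base its tests and confidence intervals on a clinic-clustered variance with a small-sample correction. One example is a leave-one-clinic-out variance with t on 35 − 1 = 34 degrees of freedom. In the simulated host layouts at ρ = 0.03 this gave levels of about 4.3% to 5.6%. Report the number of patients per arm by clinic and by region for each of these outcomes, so that readers can judge the mix for themselves, and state how matched pairs enter the variance.

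The sample size does not change, and facility is already among the extracted variables (Protocol C.7.1). Intervals become about 4% wider if the arms turn out evenly mixed, and up to about 19% wider in the host-clinic layouts. If matched pairs are positively correlated, the clustered test may be somewhat conservative.
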